10.3. Effectiveness analysis

Data name	Derivation and calculation methods	
Remission	When the CDAI score is <150, the case is regarded as remission.	
WPAI	
Q1 Do you work now? Yes, no
 
Q2 How many hours did you leave the work due to problems related to Crohn's disease over the past 7 days? () hour(s)
 
Q3 How many hours did you leave the work for a reason other than Crohn's disease such as holidays or hours for which you were off to participate in this survey over the past 7 days? () hour(s)
 
Q4 How many hours did you actually work for the past 7 days? () hour(s)
 
Q5 How much productivity was affected by Crohn's disease while you were working over the past 7 days? 0: Crohn's disease did not affect the work. 10: Crohn's disease completely interrupted the work. Based on the above, your score between 0 to 10. ()
 
Q6 How much did Crohn's disease affect various daily activities except your job over the past 7 days? ()
	

Data name	Derivation and calculation methods		
		
0: Crohn's disease did not affect daily activities.
 
10: Crohn's disease completely interrupted daily activities.
 
Based on the above, your score between 0 to 10.
	

- Absenteeism (%)

Calculate it with the following formula based on the questions (Q1 to Q6) on the above table:

$$[Q2 / (Q2 + Q4)] \times 100$$

- Presenteeism (%)

Calculate it with the following formula based on the questions (Q1 to Q6) on the above table:

$$(Q5 / 10) \times 100$$

- Overall work impairment (%)

Calculate it with the following formula based on the questions (Q1 to Q6) on the above table:

$$\{ Q2 / (Q2 + Q4) + [1 - Q2 / (Q2 + Q4)] \times (Q5 / 10) \} \times 100$$

- Activity Impairment (%)

Calculate it with the following formula based on the questions (Q1 to Q6) on the above table:

$$(Q6 / 10) \times 100$$

11. How to stratify data

Data	How to stratify
Dosage and administration	160mg→80mg→40mg once every two weeks, other
Dosing frequency (times)	≥1 and <4, ≥4 and <13, ≥13 and <26, ≥26 and <39, ≥39 and <52, ≥52 and <65, ≥65 and <78, ≥78
Total dose (mg)	<500mg, ≥500mg and <1000mg ≥1000mg and <2000mg ≥2000mg and <3000mg ≥3000mg, Unknown
Dose period	the first administration to Week 4 of administration, after Week 4 of administration to Month 3 of administration, after Month 3 of administration to Month 6 of administration, after Month 6 of administration to Year 1 of administration, after Year 1 of administration to Year 1 and Month 6 of administration, after Year 1 and Month 6 of administration to Year 2 of administration, after Year 2 of administration to Year 2 and Month 6 of administration, after Year 2 and Month 6 of administration to Year 3 of administration, Continued as of Year 3 of administration
Reason for discontinuation	Development of adverse event, lack of effectiveness, patient's wish, no visit, others
Sex	Man, women, unknown/not provided
Pregnancy/nursing	Not pregnant/nursing, pregnant, nursing, unknown/not provided
Age (in years)	<15, ≥15 and <65, ≥65, unknown/not provided
Body weight (kg)	<30, ≥30 and <40, ≥40 and <50, ≥50 and <60, ≥60, unknown/not provided
BMI(kg/m ²)	<18.5, ≥18.5 and <25, ≥25 and <30, ≥30, unknown
Duration of illness (in	<2, ≥2 and <5, ≥5 and <10, ≥10, unknown/not provided

Data	How to stratify
years)	
Indication	Crohn's disease, other, unknown/not provided
Allergy history	Without the history, with the history, unknown/not provided
Smoking history	Without the history, with the history, unknown/not provided
Details of smoking history	Smoking, only in the past (not smoking now), unknown
HBs antigen	Not conducted, conducted, unknown/not provided
Tuberculosis-test status	Not conducted, conducted
Complications	Without the history, with the history, unknown/not provided
Detailed classification of complications	Liver disorder, renal disorder, blood disorder, respiratory disorder, others
Other classification of complications	Diabetes mellitus, osteoporosis, malignant tumour, others
Medical history	Without the history, with the history, unknown/not provided
Detailed classification of medical history	Tuberculosis, non-tuberculous mycobacteriosis, interstitial pneumonia, bronchitis bacterial, aplastic anaemia, pancytopenia, malignant tumour, others
Prior medications for Crohn's disease	Without the history, with the history, unknown/not provided
Detailed classification of prior medications for Crohn's disease	Anti-TNF α drug, aminosalicylic acid products, corticosteroid, immunosuppressant, and antibiotics.
Prior treatment for Crohn's disease	Without the history, with the history, unknown/not provided
Detailed classification of prior treatment for Crohn's disease	Surgery, GCAP, enteral nutrition therapy, intravenous nutrition therapy, others
Treatment history with anti-TNF α drug	Without the history, with the history, unknown/not provided
Reason for discontinuation of treatment history with anti-TNF α drug	Lack of efficacy, adverse events, others, unknown/not provided
Concomitant medication	Without the history, with the history, unknown/not provided
Detailed classification	Aminosalicylic acid products, corticosteroid, immunosuppressant,

Data	How to stratify
of concomitant medications	antibiotics, and others
Concomitant therapy for Crohn's disease	Without the history, with the history, unknown/not provided
Detailed classification of concomitant therapy for Crohn's disease	Surgery, GCAP, enteral nutrition therapy, intravenous nutrition therapy, others
Condition/site of disease in the medical history of Crohn's disease	Anus/perianal region, rectum, stomach/duodenum, colon, jejunum/ileum, other, unknown/not provided
Intestinal complications as condition/site of disease in the medical history of Crohn's disease	Without the history, with the history, unknown/not provided
Non-intestinal complications as condition/site of disease in the medical history of Crohn's disease	Without the history, with the history, unknown/not provided
Work condition	Routinely engaged in wage labor for 35 hours or longer a week, Routinely engaged in wage labor for 35 hours or less a week, Not engaged in wage labor but do housework, shopping, childrearing, exercise, or study , Involved in daily living activities, Involved in less daily activities due to hospitalization, etc. Unknown/not provided
CDAI at the first administration	<150: remission ≥150 and <220: mild ≥220 and <450: moderate ≥450: severe Unknown/not provided
CRP	<1.0mg/dL, ≥1.0mg/dL,

Data	How to stratify
	Unknown/not provided
Self administration	Without the history, with the history, unknown/not provided

12. Data handling at test/assessment periods

12.1. Assessment period for CDAI, WPAI, CRP and non-intestinal conditions

Time allowance of assessment period with the first administration date of Humira as 1 is as follows:

Assessment period	Time Allowance(Day)
At the first administration	- 1 (scheduled date 1)
Week 4 of administration	15 - 43 (scheduled date 29)
Month 3 of administration	71 - 99 (scheduled date 85)
Month 6 of administration	169 - 197 (scheduled date 183)
Year 1 of administration	337 - 393 (scheduled date 365)
Year 1 and Month 6 of administration	519 - 575 (scheduled date 547)
Year 2 of administration	701 - 757 (scheduled date 729)
Year 2 and Month 6 of administration	883 - 939 (scheduled date 911)
Year 3 of administration	1065 - 1121 (scheduled date 1093)
At final assessment	Final assessment of each patient no matter whether the each assessment period is within Time Allowance.

The data for analysis should derive from the date closest to the scheduled date within Time Allowance. If there are more than one data dated on the same day, select the worst value.

12.2. Assessment period of endoscopy results

Time allowance of assessment period with the first administration date of Humira as 1 is as follows:

Assessment period	Time Allowance(Day)
At the first administration	- 1 (scheduled date 1)
Month 6 of administration	2 - 182 (scheduled date 183)
Year 1 of administration	183 - 364 (scheduled date 365)
Year 2 of administration	365 - 728 (scheduled date 729)
Year 3 of administration	729 - 1092 (scheduled date 1093)
At final assessment	Final assessment of each patient no matter whether the each assessment period is within Time Allowance.

The data for analysis should derive from the date closest to the scheduled date within Time Allowance. If there are more than one data dated on the same day, select the worst value.

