Smoking history, in/outpatient, past and current history of Crohn's disease, height, weight, duration of illness, complications, past illnesses, and history of allergy.

2) Previous anti-TNF α treatment of Crohn's disease

Presence/absence, history, and reasons for discontinuation of anti-TNF α treatment.

3) Previous drug treatment of Crohn's disease (treatment during the 3-month period prior to the investigation)

Presence/absence and contents of previous treatment of Crohn's disease

4) Treatment with Humira

At the time of first administration: method of administration, initial dose, and date of initial administration.

At the second administration: method of administration, dosage, and date of second administration

At the third administration and thereafter: method of administration, dosage, interval of administration, duration of administration, and reasons for change in dose or interval of administration.

Patients performing self-injection: presence/absence of written consent for transition to

self-injection, and presence/absence of self-injection transition record.

5) Treatment with antituberculosis agents

Presence/absence of antituberculosis agents, names of drugs, daily dose, and duration

6) Status of administration of concomitant drugs

Presence/absence of concomitant drug use for Crohn's disease, name of drug, route, dose, and duration.

7) Usage of non-drug treatment for Crohn's disease

Presence/absence and type of non-drug treatment, and duration.

8) Presence/absence of development of tuberculosis or serious infections

Day of examination, imaging technique, presence/absence of abnormal laboratory findings, and description of abnormal findings.

9) Crohn's Disease Activity Index (CDAI)

Evaluate at baseline and week 4, month 3, month 6, year 1, year 1.5, year 2, year 2.5 and year 3 of Humira treatment, and at the time of discontinuation of the treatment

10) Work Productivity and Activity Impairment Questionnaire: Crohn's disease (WPAI: CD)

Evaluate at baseline and week 4, month 3, month 6, year 1, year 1.5, year 2, year 2.5 and year 3 of Humira treatment, and at the time of discontinuation of the treatment.

11) C-reactive protein (CRP)

Evaluate at baseline and week 4, month 3, month 6, year 1, year 1.5, year 2, year 2.5 and year 3 of Humira treatment, and at the time of discontinuation of the treatment

12) Endoscopic examination

Date (baseline, during treatment and year 3 or after discontinuation) and endoscopic findings

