Note: Follow “12.1 Assessment period for CDAI, WPAI, CRP and non-intestinal conditions” for Time Allowance of the final assessment periods. The analysis covers only the patients with the assessment at the first administration and thereafter.

“3.2.2.1 Changes in the remission rate at each point (CDAI<150) (Observed Case)”

Patients for analysis: patients in the effectiveness analysis group

Analysis objective: to show the remission rate of CDAI at each assessment period.

Analysis item: Calculate the number of target patients, the percentage to the number of patients who achieved a remission and the number of target patients, 95%CI of the remission rate, and conduct a McNemar test for the first administration per assessment period.

Note: Follow “12.1 Assessment period for CDAI, WPAI, CRP and non-intestinal conditions” for Time Allowance of the final assessment periods. The analysis covers only the patients with the assessment at the first administration and thereafter.

For the confidence interval, use the Clopper-Pearson’s confidence interval.

“3.2.2.3 Changes in the remission rate at each point (CDAI<150) (Observed Case)”

Patients for analysis: the patients in the effectiveness analysis group whose CDAI was a remission (≥ 150) after they were started on Humira.

Analysis objective: to show the remission rate of CDAI at each assessment period of patients whose CDAI failed to achieve a remission when the administration was started.

Analysis item: Calculate the number of target patients, the percentage to the number of patients who achieved a remission and the number of target patients, 95%CI of the remission rate, and conduct a McNemar test for the first administration per assessment period.

Note: Follow “12.1 Assessment period for CDAI, WPAI, CRP and non-intestinal conditions” for Time Allowance of the final assessment periods. The analysis covers only the patients with the assessment at the first administration and thereafter.

For the confidence interval, use the Clopper-Pearson’s confidence interval.

“3.2.4.2 Endoscopy results during administration (small intestine: active phase/remission phase)”

Patients for analysis: patients in the effectiveness analysis group

Analysis objective: to show endoscopy results (small intestine) at each assessment period.

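### SAP 12.2 opens the Month 6 endoscopy window on Day 2 and leaves every scheduled date outside its own window, and remission by period is shown without the same patients' baseline

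*SAP*

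**What the plan says.** Protocol section 8(3), item 12, sets out the endoscopy data: "Date (baseline, during treatment and year 3 or after discontinuation) and endoscopic findings". The middle element has no visit, interval or frequency. Items 9 to 11 of the same list give CDAI, WPAI:CD and CRP a series of named visits.

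SAP 12.2 counts the first dose as Day 1. Besides a baseline row and a final-assessment row that ignores the windows, it defines four dated periods:

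- Month 6: "2 - 182 (scheduled date 183"
- Year 1: "183 - 364 (scheduled date 365"
- Year 2: "365 - 728 (scheduled date 729"
- Year 3: "729 - 1092 (scheduled date 1093"

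If a patient has several examinations in a window, the rule is: "The data for analysis should derive from the date closest to the scheduled date within Time Allowance". For comparison, the Month 6 row for CDAI, WPAI and CRP in SAP 12.1 is "169 - 197 (scheduled date 183".

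In SAP 13.3, chart 3.2.4.2 has "Analysis objective: to show endoscopy results (small intestine) at each assessment period", and chart 3.2.5.2 does the same for the large intestine. Both count patients examined and not examined, and give the percentages in the active and remission phases among those examined. A note limits both charts to patients with an endoscopy at first administration and thereafter. No paired comparison is specified.

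**The concern.** Endoscopy is one of the four effectiveness items in Protocol 9(1) and SAP 5.1. Columns running from Month 6 to Year 3 will be read as a course over time, and a rise in remission would be taken as mucosal improvement on long-term treatment.

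Two features weaken that reading. First, the labels do not describe when the examinations were done: an examination in the first days of treatment shows a mucosa close to its pre-treatment state, yet can be printed under Month 6, while one done at the scheduled Year 3 date is left out of Year 3. Second, each column holds whoever was examined in that period, and the plan does not show how those particular patients looked before treatment.

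**Working it through.** **1. Window lengths (SAP 12.2), length = last day - first day + 1**

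- Month 6: 182 - 2 + 1 = 181 days
- Year 1: 364 - 183 + 1 = 182 days
- Year 2: 728 - 365 + 1 = 364 days
- Year 3: 1092 - 729 + 1 = 364 days

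**2. Scheduled date against its own window**

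- Day 183 is one day after Day 182; the examination counts as Year 1.
- Day 365 is one day after Day 364; it counts as Year 2.
- Day 729 is one day after Day 728; it counts as Year 3.
- Day 1093 is one day after Day 1092; it counts in no dated period, only in the final assessment.

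**3. Same label, different meaning in SAP 12.1 and 12.2**

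The CDAI window for Month 6 is 197 - 169 + 1 = 29 days, centred on Day 183. The endoscopy window reaches only Days 169-182 of it, 14 of 29 days. For Year 3, the CDAI window is Days 1065-1121 (57 days), and the endoscopy window reaches only Days 1065-1092, 28 of 57.

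**4. How early a Month 6 result can be**

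Days 2-29 make up 28/181 = 15% of the window and Days 2-84 make up 83/181 = 46%. These are shares of days; they become shares of examinations only if the examination rate is constant.

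Because the scheduled date lies just past the window, the closest-date rule always picks the latest examination in it. That helps only patients with more than one. At an assumed 0.5 examinations per patient-year, the share of selected results from Days 2-84 is exp(-0.5 × 98/365) × [1 - exp(-0.5 × 83/365)] / [1 - exp(-0.5 × 181/365)] = 0.8744 × 0.1075 / 0.2196 = 43%, against 46% without the rule.

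The charts report mean days from the pre-treatment endoscopy to the first dose, but no timing for on-treatment examinations, so a reader could not see this. SAP 9.1 also sets a missing endoscopy day to the first of the month. That can move an examination up to 30 days earlier (day 31 to day 1), and so into an earlier window.

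**5. What timing and selection could do (assumed rates, for illustration only)**

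- Timing: suppose true remission rises linearly from 10% on Day 2 to 40% on Day 183. The Month 6 figure is then about 15% if all examinations fall on Days 2-60, 25% if spread evenly over Days 2-182, and 37% if all fall on Days 150-182.
- Selection: suppose remission is constant at 20% in patients examined for symptoms and 50% in those examined routinely. With 80% examined for symptoms, the column shows 0.8 × 20% + 0.2 × 50% = 26%. With 20%, it shows 0.2 × 20% + 0.8 × 50% = 44%. Nothing has changed in the patients.

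**The case against.** The charts are descriptive. They plan no trend test, take examined patients as the denominator and print the number not examined. They are already limited to patients with a baseline endoscopy, and SAP 12.2 has a baseline row. All of this is true. But the number not examined does not show whether those examined differ between columns, and the restriction does not require the same patients in every period. One baseline row for the whole set is not the baseline of each period's subset.

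A reader might infer that the protocol planned no endoscopy between baseline and Year 3. It did plan on-treatment endoscopy; what is missing is a date.

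A reader might also infer that the early columns hold only unscheduled examinations and Year 3 the scheduled ones, so that remission must appear to rise. The documents do not support this. Examinations after discontinuation are named in the protocol and fall in the early columns when a patient stops early. The Year 3 window excludes examinations on or after its own scheduled date. Nothing states why on-treatment examinations are done.

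**Conclusion.** The window faults stand without assumptions: Month 6 opens on Day 2, the windows are of unequal length (181, 182, 364 and 364 days), and all four scheduled dates lie outside their windows, with Day 1093 and later lost to Year 3. It also stands that charts 3.2.4.2 and 3.2.5.2 do not show the baseline status of the patients examined in each period. The SAP does make a per-period comparison with first administration for CDAI remission, by McNemar test in chart 3.2.2.1.

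That differences between periods reflect who was examined and when is a risk, not a demonstrated bias. Its size and direction cannot be computed from the documents, and the percentages in step 5 of the working rest entirely on assumed rates. The point merits correction as a matter of labelling and pairing. It does not invalidate the endoscopy data.

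**What to change.** 1. **SAP 12.2.** Start Month 6 at Day 85, the boundary already used in SAP 12.3 and 12.4, and show Days 2-84 in a separate row. Reset the limits so that each scheduled date falls inside its own window, and extend Year 3 past Day 1093. One consistent choice is to borrow the upper limits of SAP 12.1: Days 85-197, 198-393, 394-757 and 758-1121. Since examinations could then fall on either side of the scheduled date, add a rule for two that are equally distant.

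2. **Charts 3.2.4.2 and 3.2.5.2.** For each period, print the baseline active/remission status of the same examined patients as a 2x2 count with a McNemar test, as for CDAI remission. State that each period is read against its paired baseline and that periods are not compared with each other.

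The cost is SAP wording and one extra cross-tabulation per chart, with no new data. The Month 6 column gets smaller. Pairing accounts for who was examined but not for why: Protocol 8(3), item 12, lists only the date and findings, so a footnote should say that the reason for examination is not accounted for.

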In the event of a serious adverse event, and additionally, any non-serious events of malignancy in patients 30 years of age and younger, whether related to adalimumab or not, if applicable - the physician will notify the AbbVie contact person (Medical Representative in Japan) within 24 hours of the physician becoming aware of the event.

7. Duration of the investigation

Registration period: November 2011 ~ October 2013

Investigation period: November 2011 ~ March 2017

<Milestones>

Major study milestones and their planned dates are as follows:

Start of Data Collection: November 2011

Registration in the EU PAS register: Not Applicable

End of Study: The date on which statistical analysis dataset for

8. Items to be investigated

(1) Observation period

Patients will be observed for 3 years after the initiation of Humira treatment. (Patients who will continue Humira treatment for more than 3 years will also be evaluated at the end of third year to enable completion of the CRF). Patients who have been lost to follow-up during the observation period due to transfer to another hospital, discontinuation of treatment* or for other reasons will be handled as cases of discontinuation of the survey.

* A patient who has suspended Humira treatment for at least 2 months should be considered a case of discontinuation of Humira treatment that will be handled as a case of discontinuation of the survey.

(2) Registration form

Name of institution, date of completion of the registration form, name of department, name of investigator, patient ID, patient's birthdate (year/month) or age, sex, presence/absence of pregnancy/lactation (for female patients), reasons for use of Humira, date (or planned date) of initiation of Humira treatment, contraindications to use of Humira, conditions requiring special care in administration, presence/absence and effectiveness of previous treatment of Crohn's disease, history of biological therapy, presence/absence of tuberculosis or other infection (tuberculin skin test, Quantiferon test, chest X-ray, and chest CT), hepatitis B virus test (HBs antigen test), presence/absence of preventive anti-tuberculosis treatment, and baseline laboratory data (blood β-D-glucan level, peripheral blood WBC, and peripheral blood lymphocyte count).

(3) Data to be collected via CRF

1) Patient background

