	
record - 1 day for the final administration date.
 
Of note, if the final administration date is provided in the record where the final administration date of Humira has been identified according to the above rule and the “continued” checkbox is checked, follow the below:
 
 ● If the described final administration date > the final administration date imputed according to the above rule, select the imputed final administration date as the final administration date of Humira for the patient. ● If the described final administration date <= the final administration date imputed according to the above rule, select the described final administration date as the final administration date of Humira for the patient. 
If the first administration date of Humira + 1092 days < the final administration date of Humira imputed according to the above rule, select the first administration date of Humira + 1092 days as the final administration date of Humira.

Days to the final administration date of Humira	The final administration date of Humira - the first administration date of Humira + 1
Total exposure period (in years)	(Days to the final administration date of Humira + 28) / 364
Discontinued patients	
 • Patients whose final administration date of Humira comes before the first administration date of Humira + 1064 (Week 152) • Patients with a washout period with 60 days or longer. 
*The final administration date of Humira should be the administration date right before the washout of ≥ 60 days starts.

Reason for discontinuation	When a reason for discontinuation is described in the survey form, it is defined as ‘with’ reason for discontinuation. When no such description is found, it is defined as an “unknown/not provided”.
Death cases	At least a piece of data on “death” is found as the outcome of the adverse events during the safety analysis period.
Pediatrics	Patients aged < 15 years
The elderly	Patients aged ≥ 65 years

Data name	Derivation and calculation methods
Presence/absence of complications	When complication data are contained in the survey form, it should be classified as “with complications”. When the description in the survey form is not clear enough (when the check of with/without complications is not assessable or when multiple checkboxes are checked), it should be ‘unknown’ while no description should be ‘not provided’. Other cases are “no complications”.

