12.3. Assessment period for the administration status of Humira

Time allowance of assessment period with the first administration date of Humira as 1 is as follows:

Assessment period	Time Allowance(Day)
the first administration to Week 4 of administration	1-28
after Week 4 of administration to Month 3 of administration	29-84
after Month 3 of administration to Month 6 of administration	85-182
after Month 6 of administration to Year 1 of administration	183-364
after Year 1 of administration to Year 1 and Month 6 of administration	365-546
after Year 1 and Month 6 of administration to Year 2 of administration	547-728
after Year 2 of administration to Year 2 and Month 6 of administration	729-910
after Year 2 and Month 6 of administration to Year 3 of administration	911-1092
Continued as of Year 3 of administration	1093-, patients with 'continued' checked

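### Every post-baseline endoscopy window closes the day before its own scheduled date, so an examination on Day 1093 or later can never count as Year 3

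*SAP*

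**What the plan says.** SAP 12.2 counts the first dose as Day 1 and defines four post-baseline endoscopy visits. Month 6 is "2 - 182 (scheduled date 183". Year 1 is Days 183 to 364 with scheduled Day 365, and Year 2 is Days 365 to 728 with scheduled Day 729. Year 3 is "729 - 1092 (scheduled date 1093". Within each window the selection rule is: "The data for analysis should derive from the date closest to the scheduled date within Time Allowance". A last row takes the "Final assessment of each patient no matter whether the each assessment period is within Time Allowance". Charts 3.2.4.2, 3.2.5.2 and 3.2.5.3 in SAP 13.3 report active and remission phase using these windows.

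Other sections place Day 1093 at Year 3:

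- SAP 12.1 (CDAI, WPAI, CRP) gives Year 3 as "1065 - 1121 (scheduled date 1093".
- SAP 12.3 has a row for continued treatment at Year 3 that opens "1093-, patients with" the continuation box ticked. SAP 12.4 also has a row from Day 1093.
- SAP 12.5 lists Year 3 as Day 1093.
- SAP 10.1 handles a later last dose with the instruction to "select the first administration date of Humira + 1092 days as the final administration date of Humira". That date is Day 1093.

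Protocol 8(3), item 12, collects endoscopy at baseline, during treatment, and at year 3 or after discontinuation. Protocol 8(1) says patients who stay on treatment beyond three years "will also be evaluated at the end of third year to enable completion of the CRF".

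**The concern.** A rule that picks the examination nearest the scheduled date should be able to pick one done on that date. In SAP 12.2 it never can after baseline, because no window contains its own target. The first three visits pass their on-schedule examinations to the next row, and Year 3 has no next row.

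A reader of the Year 3 row would expect endoscopic status after about three years of treatment. As defined, the row can be filled by an examination done at two years, while one done at the third anniversary is left out. CDAI and endoscopy done together on Day 1096 would be Year 3 for CDAI and would have no visit row for endoscopy.

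**Working it through.** **Inputs.** Windows, scheduled dates and selection rule from SAP 12.2; comparison windows from SAP 12.1; registration period November 2011 to October 2013 from Protocol 7, taken as 1 November 2011 to 31 October 2013. Day number = date − first dose + 1.

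**1. Reproduce the scheduled dates.** Scheduled day = 7 × weeks + 1. For 26, 52, 104 and 156 weeks this gives 183, 365, 729 and 1093, as the SAP states.

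**2. Test each window against its own target.**

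| Visit | Window | Scheduled | Scheduled − window end | Row that takes the scheduled day |
|---|---|---|---|---|
| Month 6 | 2–182 | 183 | 1 | Year 1 |
| Year 1 | 183–364 | 365 | 1 | Year 2 |
| Year 2 | 365–728 | 729 | 1 | Year 3 |
| Year 3 | 729–1092 | 1093 | 1 | none |

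The baseline row, which ends on Day 1 with scheduled Day 1, is not affected.

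**3. Trace one patient (illustration).** With examinations on Days 183, 365, 729 and 1093:

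- Month 6 is empty.
- Year 1 holds Day 183 (365 − 183 = 182 days early).
- Year 2 holds Day 365 (729 − 365 = 364 days early).
- Year 3 holds Day 729 (1093 − 729 = 364 days early).
- Day 1093 appears only as the final assessment.

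**4. Calendar check, with no assumption about spread.** There are 731 possible start dates. A 29 February start is given a 28 February anniversary.

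- 12 months after first dose is Day 366 or 367, in the Year 2 window for 731 of 731.
- 24 months is Day 731 or 732, in the Year 3 window for 731 of 731.
- 36 months is Day 1097 for starts from 1 November 2011 to 28 February 2012 (120 dates) and from 1 March to 31 October 2013 (245 dates), together 365. It is Day 1096 for the other 366. It is in no visit window for 731 of 731, and lies 4 or 5 days after Day 1092.

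**5. Compare with the SAP 12.1 tolerances.** Days that 12.1 accepts for a visit but that lie outside the same visit's 12.2 window:

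- Month 6 (169–197): Days 183–197, 15 of 29.
- Year 1 (337–393): Days 365–393, 29 of 57.
- Year 2 (701–757): Days 729–757, 29 of 57.
- Year 3 (1065–1121): Days 1093–1121, 29 of 57.

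These are shares of days. They become shares of examinations only if timing is uniform over the tolerance.

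**6. Test two repairs on the same measure.** Midpoints between scheduled dates are (183 + 365)/2 = 274, (365 + 729)/2 = 547 and (729 + 1093)/2 = 911.

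| Repair | Month 6 | Year 1 | Year 2 | Year 3 |
|---|---|---|---|---|
| Boundaries moved one day, Year 3 to Day 1121 | 14/29 | 28/57 | 28/57 | 0/57 |
| Midpoint split, Year 3 to Day 1121 | 0/29 | 0/57 | 0/57 | 0/57 |

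Moving the boundaries by one day without extending Year 3 would still leave Day 1096 with no visit row. Under the midpoint split, the first, second and third anniversaries fall under Years 1, 2 and 3 for all 731 start dates.

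**The case against.** The strongest reply is that these are intervals, not visits. The cut-offs 182, 364, 728 and 1092 are the same interval ends as in SAP 12.3 and 12.4. On that reading Days 729 to 1092 are the third treatment year, and the closest-date rule simply takes the latest examination in each interval. The shared boundaries are real and probably explain where the numbers came from. But 12.3 and 12.4 label their rows as intervals, give no scheduled date, and continue with a row from Day 1093. SAP 12.2 names time points with scheduled dates and has no such row, so an examination on Day 1093 or later still has no Year 3 entry.

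Four narrower points stand at least in part:

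- Year 3 does not lose every late examination: Days 1065 to 1092, 28 of the 57 days in 12.1, still count.
- Examinations on Day 1093 or later are usually not lost, since observation ends at three years and they will often be the patient's last. But the final-assessment row mixes completers with early discontinuers and cannot stand in for Year 3.
- The calendar count concerns start dates, not patients. The protocol does not schedule endoscopy on anniversaries, and the 12.1 tolerances are not applied to endoscopy.
- The chart titles refer to results during administration, and SAP 10.1 caps the last dose at Day 1093. A window to Day 1121 would admit examinations after that cap. The final-assessment row already does so, but the SAP should say it.

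**Conclusion.** The error holds on the face of the SAP 12.2 table. All four post-baseline windows miss their own scheduled date by one day, and no examination on Day 1093 or later can count as Year 3. The third anniversary is outside the Year 3 window for every start date in the registration period, and the second anniversary is inside it for every one. That result needs only the day-numbering rule and the calendar.

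How many patients are affected is unknown, and the day shares in the working do not estimate it. The consequence is mislabelled rows in charts 3.2.4.2, 3.2.5.2 and 3.2.5.3. These are descriptive effectiveness tables with no test or confidence interval, and the safety aims are untouched. The table should be corrected, because the row that matches the protocol's one numbered endoscopy time point does not represent it.

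**What to change.** Redefine the SAP 12.2 windows so that each contains its scheduled date and Year 3 extends past Day 1093. One set that does this splits at the midpoints: Month 6 = Days 2–273, Year 1 = 274–546, Year 2 = 547–910, Year 3 = 911–1121, keeping the closest-to-schedule rule. The upper limit of 1121 is the one in SAP 12.1. The midpoints are an example; they allow wide departures (Day 273 is 90 days after the Month 6 date, Day 911 is 182 days before the Year 3 date), and narrower windows would also serve.

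State that examinations from Day 1122 count only at final assessment, and that the Year 3 row may include examinations after the Day 1093 cap on treatment.

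The cost is one SAP table, one format in the program and the production of three charts from data already collected. Examinations from Day 1122 would still have no visit row.
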